Recommend use	Consider use	Do not recommend use
High-risk of FN (>20%)	Intermediate-risk of FN (10-20%)	Low-risk of FN (<10%)

When used in recommended settings, PP-CSF has clear benefit for patients—including reducing the risk of hospitalization and death due to infection—therefore it is critically important to ensure that PP-CSF is prescribed when supported by evidence. Researchers at the Hutchinson Institute for Cancer Outcomes Research (HICOR) have conducted several retrospective studies of community practice, finding that among breast cancer patients receiving chemotherapy carrying a high or intermediate risk of FN, PP-CSF use significantly reduced the FN rates. (15) In another study of 99 community oncology practices, HICOR found that cancer patients receiving PP-CSF within 3 days of chemotherapy (i.e., as primary prophylaxis) had much lower rates of FN than situations where CSF was used after 3 days in any chemotherapy cycle or not at all. (16)

Overuse and underuse of PP-CSF both expose patients to unnecessary risks. HICOR and others have published several observational studies finding that PP-CSF is widely under and over utilized in community settings. (17, 18, 19, 20, 21) For example, in a retrospective claims analysis of 2,728 cancer patients diagnosed over a four year period in Washington State, HICOR researchers

found that PP-CSF was underutilized for patients receiving chemotherapy carrying a high FN risk: only 28% of breast cancer and 1.5% of lung cancer patients receiving high-risk chemotherapy were prescribed PP-CSF. (22) Underuse appears to be common in certain groups (the elderly, low socioeconomic status), and needlessly increases patients' risk for FN. Overuse exposes patients to side effects, primarily bone and muscle pain, and potentially high out of pocket costs, with unclear benefits. (23) The HICOR study found that over 16.5% of colorectal and 20% of non-small cell lung cancer patients received CSF alongside chemotherapy regimens carrying low risk of FN. (24)

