Sample size estimates for the intermediate risk group are based on a 50% reduction in the FN rate (the reduction observed in trials for high risk settings). This translates to a reduction in FN rate from 15% to 7.5%, when comparing intermediate risk control arm patients (no PP-CSF) to intermediate risk intervention arm patients (PP-CSF). We believe this is reasonable because the one prospective trial evaluating PP-CSF for intermediate risk chemotherapy given to women with breast cancer achieved a risk reduction of 90%, and a systematic review of clinical trials of PP-CSF use in several settings found an FN rate reduction ranging from 17% to 78%. (49) To account for possible correlation between patients within components we estimate an intraclass correlation coefficient (ICC) of 0.02. An ICC of zero corresponds to randomization of individuals rather than components; $ICC > 0$ indicates patient outcomes are more similar within a component than across components. We estimated the ICC for FN in the SWOG adjuvant breast cancer study **S0221** which has 262 clinics with 2,666 patients. (50) Using a random effects logistic regression program (component is the random effect) followed by numerical integration, the ICC was estimated to be 0.01 although statistically significantly greater than zero. We are using 0.02 to protect against underestimation of the ICC. Based on a two-sided 0.05 alpha level test, 24 components in the Intervention arm (12 components randomized to PP-CSF and 12 components to no PP-CSF among intermediate risk patients) and 45 intermediate-risk patients per component on average will give 80% power to detect whether PP-CSF reduces FN rate by 50% among patients receiving intermediate risk chemotherapy. We assume that high, intermediate and low risk patients comprise 30%, 50% and 20% at each component, respectively; this translates to a total of 90 patients per component on average. (51,52)

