Step 2: Consider the hypothesis of [Primary Objective b](#): a relative reduction in FN occurrence over 6 months from registration between the Intervention and Usual Care arms (measured by the odds ratio) over both high and intermediate risk groups. We assume FN risk of 25% for the high risk chemotherapy group (translating to a reduction in FN rate from 25% to 12.5%). Using the sample size calculations from Step 1, we employ a 3:1 randomization scheme in the main trial, resulting in 8 components randomized to Usual Care and 24 components randomized to Intervention. This translates to a total of 2,880 patients, 32 components (90 patients per component on average) for the study, and gives us 90% power for [Primary Objective b](#): to detect a 50% reduction in FN events among high and intermediate risk patients in components randomized to the guideline-based PP-CSF order Intervention vs. Usual Care. [Figure 1](#) displays a power curve for our first and second Primary Objectives.

[figure not shown]

Figure 1: Power with respect to the reduction in FN rate. The dashed vertical line is at 50% reduction. The two dashed horizontal lines are at 80% and 90% power.

Table 2 below illustrates how the required sample size for [Primary Objective c](#) and corresponding power for [Primary Objective a](#) vary according to the ICC.

Table 2. Power to detect 50% relative reduction in the FN rate. Power depends on control arm event rate and ICC.

Intra-Class Correlation	Total Sample Size	Per arm sample size		Per arm # of components		Per component sample size		Power	
		Usual Care	Order Entry	Usual Care	Order Entry	Usual Care	Order Entry	Primary Obj b	Primary Obj a
0	1536	384	1152	8	24	48	48	80%	98%
.01	1984	496	1488	8	24	62	62	80%	94%
.02	2880	720	2160	8	24	90	90	80%	90%
.03	5376	1344	4032	8	24	168	168	80%	86%

Using this sample size and with greater than 80% power, we can detect the following effect of Intervention versus Usual Care in the process outcomes of [Primary Objective a](#), namely the proportions of patients using CSF as primary prophylaxis versus other use: a reduction in CSF use from 17% to 7% among low risk patients and an increase in CSF use from 40% to 75% among high-risk patients (based on observed use in our prior observational study). (53)

In addition to the 32 study components, we will include 13 components with existing PP-CSF order entry systems in the parallel cohort to recruit 720 patients (56 patients per component on average).

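### Objective b's power applies the 50% effect of PP-CSF versus none directly to Intervention versus Usual Care in high-risk patients, with no allowance for PP-CSF already used in Usual Care

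*Combined protocol and SAP*

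**What the plan says.** Section 11.1, Step 1, sets the effect size for Objective c, which compares PP-CSF with no PP-CSF in intermediate-risk patients. It uses a 50% reduction in FN and describes it as "the reduction observed in trials for high risk settings". The figure is therefore the effect of giving the drug versus not giving it.

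Step 2 turns to Objective b, Intervention versus Usual Care in high- and intermediate-risk patients together. It assumes a 25% FN risk for high-risk chemotherapy, "translating to a reduction in FN rate from 25% to 12.5" percent. With 8 Usual Care and 24 Intervention components of 90 patients on average, it claims 90% power to show that FN is halved between these two arms.

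After Table 2, the section gives the effects detectable for Objective a with more than 80% power. One is "an increase in CSF use from 40% to 75% among high-risk patients", attributed to observed use in a prior observational study. Section 2.0 reports from the same cited study that "only 28% of breast cancer and 1.5% of lung cancer patients receiving high-risk chemotherapy were prescribed PP-CSF". Nothing in 11.1 adjusts the 50% for PP-CSF already used in Usual Care, or for Intervention use below 100%.

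**The concern.** The order system can change FN only in patients whose PP-CSF use it changes. If 40 of 100 high-risk Usual Care patients already receive PP-CSF, they already have its benefit. If some Intervention patients do not receive it, they have none. A drug that halves FN then cannot halve FN between the arms. Sections 7.1 and 11.2 let physicians change any order, so the design does not impose full uptake.

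Objective b is a primary objective with a stated power of 90%. If that power rests on an undiluted drug effect, the trial is less sensitive to the order system's effect on FN than the protocol says. A non-significant Objective b could then be given more weight against guideline-based orders than the design supports.

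**Working it through.** **Inputs, all from 11.1 unless noted.** Two-sided alpha 0.05 (stated in Step 1, assumed to carry over to Step 2); 8 versus 24 components; 90 patients per component, of whom 30% are high risk (27) and 50% intermediate (45); ICC 0.02; FN 25% to 12.5% in high risk and 15% to 7.5% in intermediate risk; PP-CSF efficacy 50%; high-risk use 40% versus 75%. Section 2.0 gives the alternative baseline use of 28% in breast cancer.

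**Step 1: reproduce the stated 90%.**
- High plus intermediate patients per component: 27 + 45 = 72.
- Design effect: 1 + 71 × 0.02 = 2.42.
- Effective sample sizes: 576/2.42 = 238 and 1,728/2.42 = 714.
- Blended Usual Care rate: (27 × 25% + 45 × 15%)/72 = 18.75%.
- Blended Intervention rate: (27 × 12.5% + 45 × 7.5%)/72 = 9.375%.
- Unpooled standard error: √(0.1875 × 0.8125/238 + 0.09375 × 0.90625/714) = 0.0276. The ratio is 0.09375/0.0276 = 3.40.
- Power from a noncentral t with 32 − 2 = 30 degrees of freedom: **90.9%**.

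The same method gives 96.2%, 93.7% and 87.9% for the other rows of Table 2, against 98%, 94% and 86%. (The power columns of Table 2 are headed Objectives b and a, while the text assigns 80% to c and 90% to b; the text is followed here.) Normal-approximation formulas give 92.5% (unpooled), 95.5% (pooled) and 96.9% (log odds ratio). The stated power is thus reproduced with the full 50% in both risk groups, so no dilution was built in.

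**Step 2: reduction implied by uptake.** Let e be efficacy, u the use in Usual Care and v the use in Intervention. If users and non-users have the same underlying risk, the relative reduction is 1 − (1 − v·e)/(1 − u·e).

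| Use, Usual Care vs Intervention | Efficacy | High-risk reduction |
|---|---|---|
| 40% vs 75% | 50% | 1 − 0.625/0.80 = 21.9% |
| 28% vs 75% | 50% | 1 − 0.625/0.86 = 27.3% |
| 40% vs 100% | 50% | 1 − 0.50/0.80 = 37.5% |
| 28% vs 100% | 50% | 1 − 0.50/0.86 = 41.9% |
| 40% vs 75% | 17% / 78% (review range in 11.1) | 6% / 40% |
| 40% vs 75% | 90% (single intermediate-risk trial) | 49% |
| 0% vs 100% | 50% | 50% |

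In absolute terms, the first row is 25% to 19.5% if 25% is the Usual Care risk, or 20% to 15.6% if 25% is the untreated risk.

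**Step 3: efficacy needed for a 50% between-arm reduction.**
- 40% versus 75% use: 1 − 0.75e = 0.5(1 − 0.40e), so e = 0.5/0.55 = 91%.
- 40% versus 100% use: 1 − e = 0.5(1 − 0.40e), so e = 0.5/0.80 = 62.5%.

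**Step 4: Objective b power, changing only the high-risk rates.** Intermediate risk stays at 15% to 7.5%, and ICC at 0.02.

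| High-risk rates | Blended rates | Blended reduction | Power, t method | Power, z formulas |
|---|---|---|---|---|
| 25% to 12.5% (plan) | 18.75% vs 9.4% | 50% | 91% | 93-97% |
| 25% to 19.5% (40% vs 75% use) | 18.75% vs 12.0% | 36% | 64% | 67-74% |
| 20% to 15.6% (40% vs 75% use) | 16.9% vs 10.5% | 37.5% | 63% | 65-73% |
| 25% to 15.6% (40% vs 100% use) | 18.75% vs 10.5% | 44% | 82% | 84-90% |
| 20% to 12.5% (40% vs 100% use) | 16.9% vs 9.4% | 44% | 78% | 81-88% |

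**The case against.** **75% is not a forecast.** It is worded as an effect that Objective a can detect, and observed prior use can anchor only the 40%. This stands, and it is why the result is given for Intervention uptake from 75% to 100%. Even at 100%, the plan's efficacy yields 37.5%, not 50%.

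**A reader might infer that a 50% between-arm reduction could never be reached.** The documents do not support that. Efficacy of 62.5% with 40% versus 100% use gives 50% and lies inside the 17-78% review range quoted in 11.1. The assumption is optimistic and inconsistent with the plan's own 50% efficacy, but not impossible.

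**A reader might also infer that the plan calls Usual Care untreated.** It does not. The point is that 25% to 12.5% follows from 50% efficacy only with 0% versus 100% use.

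**The inputs are uncertain.** The 40% sits beside 28% in Section 2.0 from the same cited study, and every high-risk regimen in Appendix 18.1 is a breast regimen. The wording in 11.1, primary prophylaxis versus other use, could even mean a share of CSF users. The text also leaves open whether 25% is untreated or Usual Care risk. All this stands and belongs in the fix; at 50% efficacy, neither baseline figure restores 50%.

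**The stated power is conditional, and the ICC is cautious.** The plan gives power to detect a 50% reduction, includes a power curve against the size of the reduction, and uses twice the estimated ICC of 0.01. This is fair. At ICC 0.01 the design effect is 1 + 71 × 0.01 = 1.71, and 25% to 19.5% gives about 79% by the t method (82-87% by z formulas). But the only justification offered for 50% is PP-CSF versus none, and Section 11.7 expects the same relative Intervention effect in both risk groups.

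**Conclusion.** The concern holds in a limited form. Step 2 carries a drug effect into a comparison of order systems without allowing for the Usual Care use that the same section reports. At 50% efficacy, the high-risk reduction is about 22% with 40% versus 75% use, 27% with baseline use of 28%, and 37.5% with full Intervention uptake from 40%. Objective b power at ICC 0.02 is then about 63-64% by the method that reproduces the plan (65-74% by z formulas), or about 78-90% across methods with full uptake.

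These figures assume that efficacy is 50%, that users and non-users share the same underlying risk, and that 40% is a share of all high-risk patients. The 22% applies to the high-risk group only, not to Objective b as a whole. The power figures keep the plan's 15% to 7.5% for intermediate-risk patients across the whole Intervention arm, which is a separate question because half of those components default to no PP-CSF. They show the effect of this one assumption and should not be read as Objective b's final power.

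**What to change.** In Section 11.1:

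1. State that the 50% is the effect of PP-CSF versus none, not of Intervention versus Usual Care.
2. State whether 25% is the untreated or the Usual Care FN risk in high-risk patients.
3. Reconcile the 40% with the 28% in Section 2.0, and say which patients form the denominator.
4. Replace 25% to 12.5% with between-arm rates derived from stated uptake in each arm and stated efficacy. With 40% versus 75% use and 50% efficacy these are 25% to 19.5%, or 20% to 15.6% if 25% is the untreated risk.
5. Restate Objective b's detectable reduction and power for Intervention uptake from 75% to 100%, and note that the result still depends on the separate intermediate-risk assumption.

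The endpoint, the model and enrolment do not change. The cost is one recalculation, some wording, and a stated power lower than 90%.

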11.2 Analysis of Primary Objectives

Primary prophylactic CSF (PP-CSF) is defined as CSF administered with the first cycle of systemic therapy, within 24 to 72 hours after the initial therapy dose. PP-CSF use is observed and reported.

The natural history of FN is cycle specific: a patient can develop FN within 3 to 10 days after the initial administration of chemotherapy, when their neutrophil count reaches its nadir. Therefore initial data collection is generally based on cycles rather than calendar time.

This study uses a cluster randomized design: the study intervention is administered at the component level, rather than the patient level. The study intervention is to change the component's standing order system to reflect guidelines-based PP-CSF use, or to not change to the order system. All patients at a given component will be subject to the same order system, regardless of study participation; only registered patients will have their data reported to the study. Treating physicians at each component may change any individual patient's orders at any time, at their discretion.

The initial treatment regimen is defined as the systemic treatment intended for cancer treatment, at registration as determined by the treating physician and as defined in [Section 18.1](#). Patients are followed through 12 months after registration, regardless of treatment status. This protocol does not direct systemic cancer treatment therapy.

Given the cluster randomization design, we will estimate the intraclass correlation coefficient (ICC) and adjust for it in all analyses.

- a. *Primary Objective a: To compare the use of primary prophylactic colony stimulating factor (PP-CSF) according to recommended clinical practice guidelines between patients registered at Intervention components versus Usual Care components.*

PP-CSF is by definition administered at the start of the first cycle of chemotherapy; this objective will evaluate the use of CSF during the first cycle of systemic therapy.

Randomization is at the component level; outcomes are measured at the patient level. Since patients are nested within components, this structure will be

accounted for by using mixed effects regression models including a random effect for component. Among high risk and low risk patients, separate mixed effects logistic models will be fit to assess the effect of the intervention on PP-CSF use. In addition to including a random effect for component and an indicator variable for randomized group (Intervention versus Usual Care), we will adjust for component-level characteristics and patient-level clinical and demographic variables.

If the quality of the component application data is acceptable (proportion of missingness $\leq 10\%$), we will descriptively compare trends in PP-CSF prescribing prior to the start of the study versus after the start of the study, in order to determine if there is a change in PP-CSF prescribing at the components based on their participation in the study (i.e., a Hawthorne effect).

b. *Primary Objective b: To compare the rate of febrile neutropenia (FN) between patients registered to Intervention components versus Usual Care components.*

The rate of FN will be evaluated at 6 months post-registration. The risk of FN is greatest during the first cycle, but patients are still at risk throughout therapy. The FN risk levels assigned to the various systemic therapies in this protocol are based on risk for the duration of treatment, and so the analysis will look at the FN rate at 6 months into therapy.

Randomization is at the component level; outcomes are measured at the patient level. Since patients are nested within components, this structure will be accounted for by using mixed effects regression models including a random effect for component. A mixed effects logistic model will be used to assess the effect of the intervention on FN occurrence within 6 months from registration. In addition to including an indicator variable for randomized group (Intervention versus Usual Care), we will adjust for component-level characteristics and patient-level clinical and demographic variables. We will also descriptively compare time to FN occurrence between Intervention and Usual Care practices using Kaplan-Meier plots.

In a secondary analysis, we will do a three-way comparison among the intermediate risk patients, comparing Usual Care to each of the two Intervention groups – PP-CSF and no PP-CSF. For this analysis, we will fit a similar model as above, but instead of an indicator variable for randomized group (Intervention versus Usual Care), we will include a categorical variable for randomized group with three levels: (i) Usual Care (reference), (ii) Intervention – PP-CSF, and (iii) Intervention – no PP-CSF.

Subgroup analysis: We will assess the magnitude of intervention effect in subgroups and how that effect changes across subgroups (after stratification by subgroup). We will use interaction tests and construct a forest plot to display the heterogeneity in intervention effects across subgroups (details in [Section 11.7](#)). Subgroup analyses will be performed for each cancer type, level of FN risk, race and the following variables: race (African-American, white, other); age (categorized as < 50, 50-59, 60-69, 70-79, 80+ years); non-cancer comorbidity performance status (Zubrod), stage of cancer at enrollment (distant, local, regional). (54, 55, 56, 57, 58, 59)

c. *Primary Objective c: To compare the rate of FN among intermediate risk patients registered to Intervention components by component treatment assignment (administer PP-CSF to intermediate risk patients versus not).*

The rate of FN will be evaluated at 6 months post-registration. The risk of FN is greatest during the first cycle, but patients are still at risk throughout therapy. The FN risk levels assigned to the various systemic therapies in this protocol are based on risk for the duration of treatment, and so the analysis will look at the FN rate at 6 months into therapy.

As before, since patients are nested within components, a mixed effects logistic model with a random effect for component will be used to assess the effect of prescribing CSFs as primary prophylaxis on FN occurrence within 6 months from registration. In addition to including an indicator variable for randomized group (CSFs prescribed as primary prophylaxis or not), we will adjust for component-level characteristics and patient-level clinical and demographic variables.

Subgroup Analysis: Among intermediate risk patients registered to Intervention components, we will assess the magnitude of PP-CSF effect in subgroups defined by FN risk factors and how that effect changes across subgroups (after stratification by subgroup). We will use interaction tests and construct a forest plot to display the heterogeneity in PP-CSF effects across subgroups (details in [Section 11.7](#)). Subgroup analyses will be performed for the following risk factors: age (categorized as < 50, 50-59, 60-69, 70-79, 80+ years), race, comorbid conditions, poor performance status, prior chemotherapy, serum albumin abnormal liver function, poor renal function, low baseline WBC, chemotherapy dose intensity, type of chemotherapy.

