11.9 Interim Analysis

An interim analysis for Primary Objective c will be conducted. This may allow early termination of part of the sub-trial (e.g. a single arm) in intermediate risk patients due to demonstrated efficacy or futility of PP-CSF in an interim analysis of FN incidence. Interim

analyses will be conducted when 360 patients (24 clinics * 15 patients/per clinic) and 650 patients (24 clinics * 27 patients/per clinic) in the intermediate risk group at Intervention clinics have complete outcome information, i.e., their outcomes have been observed and classified as positive or negative; these sample sizes correspond to 50% and 75% information. Information is calculated based on the ICC of 0.02, and therefore it accumulates faster than does patient accrual. We will use O'Brien-Fleming stopping rules, which employ conservative criteria for termination and result in a minimal loss of power. Pre-specified decision criteria will be as follows: for 80% power, the cumulative alpha spent at the 50%, 75%, and final time points will be 0.003, 0.019, and 0.050, respectively. The corresponding p-value cutoffs for frequentist inference will be 0.003, 0.018, and 0.044, respectively. Futility analysis will also be conducted at the same time points. If the p-value is >0.936, >0.292 or >0.044, respectively, or if the odds ratio is in the opposite direction as that hypothesized, consideration will be given to declaring futility.

The interim analyses will be reported to the DSMC, who will make a recommendation to continue or stop the sub-trial. If early termination of the sub-trial for Primary Objective c occurs, the DSMC will be consulted about next steps regarding accrual to meet sample size requirements for Primary Objectives a and b.

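### The primary mixed logistic models name no small-sample inference for 24 or 32 components; with default large-sample tests, a nominal 5% test for Objective c runs at about 6-7%.

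*Combined protocol and SAP*

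**What the plan says.** For Objectives a and b, section 11.2 states that clustering is "accounted for by using mixed effects regression models including a random effect for component". For Objective c, "a mixed effects logistic model with a random effect for component will be used to assess the effect of prescribing CSFs as primary prophylaxis". The section also says that the ICC will be estimated and adjusted for in all analyses, and that unlisted component-level characteristics will be covariates. It does not say whether the treatment effect is tested by a Wald or a likelihood-ratio test, against which distribution, or with what degrees of freedom. Robust variance is mentioned only for the secondary Poisson models in 11.3.

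The number of components is small. For Objective c, section 11.1 has "Based on a two-sided 0.05 alpha level test, 24 components in the Intervention arm", split 12 and 12, with 45 intermediate-risk patients each and 80% power. For Objectives a and b, a 3:1 scheme is used, "resulting in 8 components randomized to Usual Care and 24 components randomized to Intervention". On the ICC, the source trial gave 0.01, significantly above zero, and "We are using 0.02 to protect against underestimation of the ICC".

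Section 11.9 plans looks at 15 and 27 patients per component before the final 45, and states: "The corresponding p-value cutoffs for frequentist inference will be 0.003, 0.018, and 0.044, respectively".

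**The concern.** Treatment is allocated to components, so the treatment effect is a contrast between components. Its precision depends on a between-component variance that has to be estimated from 24 or 32 units. Large-sample inference from a mixed logistic model treats that variance as known. With this few components the standard error tends to be too small and the normal reference too narrow. Estimating the ICC and adjusting for it does not remove the problem, because the problem is the uncertainty in that estimate.

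At stake is the 5% error rate of every primary test. For Objective c it is also the error spent at looks that may end part of the sub-trial. A plan that leaves the test open also allows the method to be chosen once results are visible, and a p-value near 0.05 could change its verdict with that choice.

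**Working it through.** **Inputs from the documents.** Two-sided alpha 0.05; 12 vs 12 components of 45 for Objective c; 15% vs 7.5%; ICC 0.02 (estimate 0.01). For Objectives a and b, 8 vs 24 components of 90 patients, split 30/50/20%, that is 27 high, 45 intermediate and 18 low risk. Control FN rate for Objective b: (27 × 25% + 45 × 15%)/72 = 18.75%. Control PP-CSF use for Objective a: 40% (high risk) and 17% (low risk).

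**Assumptions, not in the documents.** Beta-binomial variation between components; coefficient of variation (CV) of component size 0 to 0.6; 0 to 2 component covariates; ICC for PP-CSF use 0.02 to 0.2.

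**1. The plan's own figures use a normal reference.**
- Design effect 1 + 44 × 0.02 = 1.88. Effective n per arm 12 × 45/1.88 = 287.2.
- Unpooled SE = √[(0.15 × 0.85 + 0.075 × 0.925)/287.2] = 0.0262. Then 0.075/0.0262 = 2.86, and power = Φ(2.86 − 1.96) = 81.7%. With the pooled variance under the null it is 81.3%, or 79.9% at the final cutoff of 0.044. The plan states 80%.
- Information at the looks: 12 × 15/1.28 = 140.6 and 12 × 27/1.52 = 213.2, which are 49% and 74% of 287.2 (plan: 50% and 75%).
- O'Brien-Fleming-type spending gives 0.0031, 0.0193 and 0.0500, with nominal p 0.0031, 0.0183 and 0.0440. These match 11.9.

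**2. Simple tail check.** If the statistic follows t with components minus 2 df, the cutoff of 1.96 has true size 6.3% (22 df) or 5.9% (30 df).

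**3. Null simulation.** Random-intercept logistic model, maximum likelihood, Wald z at nominal 5%, about 20,000 data sets per row (Monte Carlo SE about √(0.069 × 0.931/20,000) = 0.2 points).

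| Setting | Wald z | t reference |
|---|---|---|
| c, ICC 0.02 | 6.9% | 5.4% |
| c, ICC 0.01 | 6.4% | 5.2% |
| c, ICC 0 | 4.5% | 3.4% |
| c, ICC 0.02, size CV 0.6 | 7.8% | 6.4% |
| c, ICC 0.02, two covariates | 8.1% | 6.5% |
| b, ICC 0.02 | 6.7% | 5.7% |
| b, ICC 0.01 | 6.6% | 5.5% |
| b, ICC 0.02, size CV 0.6 | 6.8% | 5.9% |
| b, ICC 0.02, two covariates | 7.7% | 6.5% |
| a, ICC 0.02 (high / low risk) | 5.9 / 5.9% | 5.0 / 4.9% |
| a, ICC 0.10 (high / low risk) | 6.7 / 6.3% | 5.6 / 5.3% |
| a, ICC 0.20 (high / low risk) | 7.3 / 7.7% | 6.2 / 6.5% |

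A separate implementation gave 7.1% (c, ICC 0.02), 6.2% (c, ICC 0.01) and 7.1% (b). Likelihood-ratio tests gave 5.8-6.7%.

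**4. Interim looks, Objective c** (Wald z, 15, 27 and 45 patients per component, ICC 0.02, 40,000 data sets).

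| Look | Nominal p | Simulated level | Planned cumulative | Simulated cumulative |
|---|---|---|---|---|
| 1 | 0.003 | 0.0043 | 0.003 | 0.0043 |
| 2 | 0.018 | 0.0289 | 0.019 | 0.0301 |
| Final | 0.044 | 0.0638 | 0.050 | 0.0729 |

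Other implementations put the first look at 0.0028 and 0.0036 at ICC 0.02, and at 0.0018 and 0.0023 at ICC 0.01. Two covariates plus CV 0.6 raised it to 0.0059. The second look ranged from 0.023 to 0.031.

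**5. With a t(22) reference.** Cumulative levels become 0.0011, 0.0191 and 0.0560. Power for Objective c falls from 81.7% to 78.2% (noncentral t, alpha 0.05). Simulated at the 0.044 cutoff it falls from 82.9% to 80.0%.

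**The case against.** The strongest reply is that the plan never says Wald z. A likelihood-ratio test fits the text equally well and runs closer to nominal, at about 6-6.5% for Objective c. At ICC 0 the Wald test is slightly conservative. The excess in the base case is only 1-2 points, the higher figures need inputs that the documents do not give, and section 11.9 leaves stopping to a DSMC recommendation. All of this stands, and it makes the result conditional. It does not remove it: the plan's own ICC estimate is above zero, both default tests are liberal there, and nothing in the text excludes them.

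A reader might also infer that the first interim boundary is hit hardest, because it lies far in the tail: 2 × P(t22 > 2.968) = 0.0071, more than twice 0.003. The documents do not support that reading. At 15 patients per component and ICC 0.02 the design effect is only 1.28, so most of the variance is binomial sampling and t(22) describes the statistic poorly. Simulation puts this look at about 0.002-0.004. It reaches about twice nominal only with assumed covariates and uneven sizes together.

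**Conclusion.** The omission is real and bears on all three primary objectives. Under default large-sample inference, Objective c has a true size of about 6-7% with Wald z at ICC 0.01-0.02, or about 6-6.5% with a likelihood-ratio test. Objective b is about 6.5-7%. Objective a is about 6% at ICC 0.02, and more if the ICC for PP-CSF use is larger, which is an assumption. About 8% is reached for Objective c with size CV 0.6 or two component covariates. Those values are also assumed, although the plan allows both features by leaving site accrual uncapped and the covariates unlisted.

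The first-look cutoff is roughly at its nominal level (up to 0.006 under the added assumptions). The excess falls at the second look (0.023-0.031 against 0.018) and the final look, for an overall size of about 7% against 5%. It would be too strong to say that every primary test exceeds 5% whatever is done: that requires default inference and a non-zero ICC.

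**What to change.** - In 11.2, state that the treatment effect in each primary model is tested with a small-sample method. A component-level permutation test that respects the stratified randomisation is preferable. Section 6 describes the strata only for Usual Care versus Intervention, so the scheme behind the 12 vs 12 allocation should be stated too.
- The alternative is t inference with component-based degrees of freedom. It is less complete: a plain t reference still leaves about 6-6.5% with uneven sizes or two covariates.
- In 11.9, read the p-value cutoffs from the same test, and note that a plain t(22) reference is conservative at the first look (about 0.001 or less against 0.003).
- Pre-specify the component-level covariates. Which ones to include is a modelling choice; what matters is that the list is short and fixed in advance.
- Restate Objective c power as about 78%.

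The cost is analysis wording and about 3-4 points of power for Objective c (81.7% to 78.2%). No new data are needed, so the closure of accrual is no obstacle.
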